2 ELIGIBILITY ASSESSMENT AND ENROLLMENT

The verification of eligibility and enrollment of subjects will follow the procedures that are outlined below and summarized in the two flow diagrams at the end of the section (Figures 1 and 2). A nurse will assess the eligibility of PCa patients, and an interviewer determines the eligibility of population-based controls. Eligible candidates will be offered an incentive with a monetary value of up to \$75 to participate in the study.

October 28, 2004 05-C-N021

ENROLLMENT OF CASES

Cases will be identified through resources including, but not limited to, daily afternoon visits, or phone calls, to the pathology departments to identify all cases diagnosed that day with PCa. We will also review the weekly lists of scheduled surgeries. We have established active collaborations with the Departments of Pathology and Urology at the University of Maryland and the Baltimore Veterans Affairs Medical Center to maximize our ability for recruitment of new PCa cases.

Case recruitment will follow the new HIPAA regulations ("HIPAA Privacy Rule"). However, to better assess eligibility, we will review medical and pathology records, medical examiner reports, cancer center registries and hospital databases. Our contractor has been granted a HIPAA waiver to perform the aforementioned study activities for our protocol.

We have obtained an agreement with the Departments of Urology and the treating physicians that they will put a note into the medical record of severely ill PCa patients. The note will indicate that we should not contact this patient because of health concerns. If no such note is found in the medical record, we will proceed and contact eligible patients. If a note is found, the interviewer will record the reason for refusal on the eligibility record, in addition to age, race, and family history. Other physicians who see prostate cancer patients will contact us through their staff.

After the eligibility has been confirmed, a nurse will contact patients to get both informed consent and authorization to obtain, use and disclose protected health information for research. A trained interviewer and phlebotomist will administer the questionnaire to those who consented. After the interview, blood will be collected. The investigators will make every effort to obtain informed consent and administer the questionnaire well in advance of either a scheduled surgery or an alternative treatment such as radiation or hormone therapy. Most of the patients will not be rushed to surgery. The disease is detected by needle biopsy and patients may seek a second or third opinion before they decide on a treatment option. Thus, we will have the opportunity of recruiting most patients weeks or months before either a surgery is scheduled or an alternative treatment will start. It is always at the discretion of the patient to give informed consent on one day but to have the interview or the blood collection on another day that is convenient for him. In the situation where we cannot get access to an eligible patient well in advance of surgery, we will approach the patient up to one day before surgery to seek consent. We will offer to administer the questionnaire and obtain blood after the surgery. However, if the patient wishes to be interviewed and have the blood drawn at the same day when he gives informed consent, we will do so. If we would limit our access to surgery patients because of a longer waiting period where we do not approach eligible cases prior to surgery, it could seriously compromise our ability of collecting the number of fresh-frozen tumor specimens that are needed for our research study.

October 28, 2004 05-C-N021

PROCEDURES

- 1. Interviewer obtains patient's name, location and physician's name
- 2. Interviewer screens medical record for eligibility. If eligible, record age, race and family history. Record reasons for ineligibility. Also record histology of tumor
- 3. Interviewer obtains a non-objection statement from the treating physician to contact the patient. If physician refuses, interviewer records reason for refusal on eligibility record, in addition to age, race, and family history of PCa
- 4. Interviewer contacts case and obtains informed consent and authorization to obtain, use and disclose protected health information for research
- 5. If patient refuses (either right away or repeatedly delaying consent [failure to make commitment in response to 3 requests]), then record brief information from medical record about family history, age, and race, on eligibility record. If subject requests that no such information will be kept on file, we will not record this information and will delete any information that already exists on file. However, we will keep the medical record number to avoid re-contacting those subjects that refused to participate in our study
- 6. Perform interview and complete questionnaire for those consented. The interviewer will give a copy of the questionnaire to the patient before the interview begins. The patient will have the opportunity to read a question while being interviewed. The last section of the questionnaire which is examining sexual history is self-administered. Provide incentive of \$25
- 7. Collect 45 cc of blood in one 15 cc red top tube and three 10 cc green top tubes. Place tubes in a thermos for short-term storage and transport
- 8. Collect urine (50 ml)
- 9. Provide incentive of \$25
- 10. Blood (separation of serum and blood clot; buffy coat; plasma and red blood cells) and urine to be processed within 8 hours at the University of Maryland Department of Pathology
- 11. Review pathology report to confirm diagnosis and abstract pathological data
- 12. Request confirmation of the pathology for the specimens that are collected from radical prostatectomy.
- 13. Request part of tumor block and frozen tumor, if available, for storage
- 14. If subject is re-contacted at a later time for additional phlebotomy, then an additional \$25 incentive is given. If subject is contacted for additional questionnaire information, then no additional award is given

ENROLLMENT OF POPULATION-BASED CONTROLS

Identify subjects through Department of Motor Vehicles database, frequencymatched on age and race. Search the Internet for the home phone number. We will contact the person by phone to verify eligibility and the willingness to participate in the study. We will obtain both informed consent and authorization to obtain, use and disclose protected health information for research at a location that is convenient to the subject. A trained interviewer and phlebotomist will contact the person and administer the

NCI IRB Approval:	October 28, 2004
Protocol Number:	05-C-N021

questionnaire to those who consented. Blood and urine will be collected either at the interview or at a separate appointment.

PROCEDURES

- 1. An introductory letter is sent to a prospective subject to notify him of the study
- 2. The subject is contacted by phone to explain the study and how he was selected, and to request participation. The permission to interview the person is obtained. If person refuses to participate (either right away or repeatedly delaying consent [failure to make commitment for 3 requests]), then record brief information about age, race, and family history of lung and prostate cancer. If subject refuses to give the information and also requests that no such information will be kept on file, we will not record this information and will delete any information that already exists on file. However, we will keep a DMV ID number to avoid re-contacting those subjects that refused to participate in our study
- 3. Obtain informed consent and authorization to obtain, use and disclose protected health information for research. This is done either at the study office, or other locations such as person's home or person's work location. If person refuses (failure to make commitment for 3 requests), then record brief information about age, race, and family history of lung and prostate cancer. If subject refuses to give the information and also requests that no such information will be kept on file, we will not record this information and will delete any information that already exists on file. However, we will keep a DMV ID number to avoid re-contacting those subjects that refused to participate in our study
- 4. Perform interview and complete questionnaire. This is done either at the study office, or other locations such as person's home or person's work location. The interviewer will give a copy of the questionnaire to the subjects before the interview begins. Subjects will have the opportunity to read a question while being interviewed. The last section of the questionnaire which is examining sexual history is self-administered. Provide incentive of \$25
- 5. Collect about 55 cc of blood. One 15 cc red top tube, three 10 cc green top tubes and one 10 cc red-green top tube. Place tubes in a thermos for short-term storage and transport
- 6. Collect urine (50 ml)
- 7. Provide incentive of \$25
- 8. Blood (separation of serum and blood clot; buffy coat; plasma and red blood cells) and urine to be processed within 8 hours at the University of Maryland, Department of Pathology. Four 2 cc aliquots of heparinized blood will be preserved. The red-green top tube will be sent to LHC within 24 hours for lymphocyte culture
- 9. If subject is re-contacted at a later time for additional phlebotomy, then an additional \$25 incentive is given. If subject is contacted for additional questionnaire information, then no incentive is given

RE-CONTACTING SUBJECTS FOR ADDITIONAL INFORMATION OR BLOOD

NCI IRB Approval:	October 28, 2004
Protocol Number:	05-C-N021

[figure not shown]
The interviewer who administered the questionnaire will be the person who will recontact the subject. This re-contact will not involve a script because of the large number of possible circumstances. Subjects will be re-contacted only under certain conditions. The conditions are as follows:

- 1. If there is missing information in the questionnaire
- 2. If the provided information is illegible
- 3. If there is a discrepancy between questionnaire and medical record information
- 4. If there is an obvious inconsistency in the answers to two similar questions in the questionnaire
- 5. If an insufficient volume of blood has been collected
- 6. If there has been mishandling of a blood sample in the laboratory
- 7. If there has been an accident leading to the loss of a blood sample
- 8. If the analysis of a blood sample returns a highly unusual result

We will not contact subjects, who refused to answer questions during the interview process, for responses to those questions they refused. Missing information due to refusal will be marked as such in the questionnaire. We will also not contact a person who failed to complete the sexual history part of the questionnaire.

PROCEDURES

- 1. Subject is contacted by phone, or by letter, notifying him of the need for additional information or blood. If notified by letter, we will include a postage paid envelope and form to be returned if the subject does not want to be contacted
- 2. If only additional information is requested, we will ask the subject by phone for the information. This will be done at the first phone contact, or two weeks after the notification letter was sent out
- 3. If subject agrees, then additional phlebotomy can be done at the home or in the hospital, whichever is convenient

[figure not shown]
[figure not shown]

Figure 2: Flow Diagram for the Accrual of Controls

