1.1 STUDY OBJECTIVES

PRIMARY OBJECTIVE

We will examine the association of allele variant genes with PCa risk. The key aim is to examine pathways in relation to PCa, e.g., host defense, inflammation pathways. Within cases, we will examine the relation of genetic variants to molecular, clinical, and prognostic endpoints. The objective will be accomplished with 1) genotype analysis of blood DNA from 1000 cases and 1000 controls and 2) collection of data from questionnaires, medical and pathology records, and the National Death Index. We are testing the hypothesis that susceptibility to nonhereditary PCa is modified by allele variant genes that modulate host defense, inflammation, hormone-stimulated survival and proliferation of mutant cells, the DNA repair capacity, or tumor angiogenesis. The susceptibility may vary by race and lifestyle (gene-environment interaction).

SECONDARY OBJECTIVES

- We will develop gene expression profiles of 60-100 tumors, and will compare gene expression in low-stage and high-stage tumors of African-Americans with gene expression in same stage tumors of Caucasians. The objective is to find gene expression profiles of cancerous and non-cancerous prostate tissue that are characteristic for the disease in African-American men. *We are testing the hypothesis that the molecular signature of primary prostate tumors is different between African-American and Caucasian men. The gene expression profile of African-Americans is associated with an early onset of the disease, a more rapid cancer progression and poor outcome.*
- We will examine the gene expression profiles of tumors from current (n = 10-15) and never smokers (n =10-15). We are testing the hypothesis that current smoking induces a gene signature of tumor progression that reveals the mechanism by which tobacco smoke promotes prostate cancer progression.
- We will determine IGF-1 serum concentrations in our study population and compare gene expression profiles of about 10-15 low-stage tumors from patients with blood IGF-1 levels in the extreme quartiles, respectively. We are testing the hypothesis that a high IGF-1 blood concentration modulates gene expression in primary tumors. The molecular profile is associated with disease progression and poor outcome.

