1.2 BACKGROUND AND RATIONALE

1.2.1 RATIONALE FOR CONDUCTING THE STUDY IN THE GREATER BALTIMORE AREA

Our goal is to identify and compare genetic risk factors in two ethnic groups, African-Americans and Caucasians. The two hospitals that we chose to recruit PCa patients are located in Baltimore City, Maryland. Baltimore has a large African-American population, and we estimate that about half of the PCa patients at the two hospitals will be of African-American descent. The study will be supported by an existing epidemiologic infrastructure with our contractor at the University of Maryland and an established relationship between our group and the Departments of Pathology at the two hospitals. The Laboratory of Human Carcinogenesis is currently conducting a lung cancer case-control study at the same hospitals and is recruiting population-based controls to match the cases. The controls recruited for the lung study meet the eligibility criteria of the proposed PCa study. The mean and median age of male cases in the lung cancer study is 65-66 years. If the age distribution of the PCa patients does not change in the next 5 years, we expect about the same mean and median age for the PCa cases, as indicated by hospital records and cancer registry data (Tables 1 and 2). Such an age distribution will allow the matching of PCa cases with population-based controls using the established resources. The recruitment will be accomplished by over-sampling of male controls under the current protocol for the lung study. PCa cases will be identified primarily by PSA screening. Needle biopsies are taken to confirm the presence of cancer in screen-positive patients. We expect to recruit up to 25 patients per year, who present with cancer in a needle biopsy and undergo a radical prostatectomy prior to chemotherapy, radiation, or hormone therapy. The remaining patients will have chemotherapy, radiation, or hormone therapy, where only blood samples but no tumor specimens will be collected.

Calendar Year 2001		
Age (yrs) Number of Patien		
40-49	10	
50-59	67	
60-69	126	
70-79	93	
80+	17	
Total	313	

Table 1: Age	Distribution (of PCa Patients	s at the Two	Participating	Hospitals
10010 11150	Distribution	of I Cu I unont	jui ille 1 mo	i untroiputing	inoppituito

	University of Maryland Medical Center Calendar Year 2001			
Age (yrs)	African-American	Caucasian	Total	
40-49	2	5	7	
50-59	21	27	48	
60-69	22	42	64	
70-79	18	19	37	
80+	2	2	4	
Total	65	95	160	

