2.1.1 INCLUSION CRITERIA

CASES

- 1. Has been diagnosed with PCa within the last two years
- 2. Pathological diagnosis of PCa made
- 3. Must reside in Baltimore City or contiguous metropolitan counties, Anne Arundel and Prince George's counties, Eastern Shore, western and northern Maryland, or adjacent counties in Pennsylvania, Delaware, Virginia, or Washington DC area
- 4. Has a residential working phone within his home
- 5. Was born in the United States
- 6. Of African-American or Caucasian descent, and age 40 to 90 years
- 7. Speaks English well enough to be interviewed
- 8. Is physically and mentally capable of performing the interview
- 9. Never has been interviewed as a control for the study
- 10. A non-objection statement to contact the patient has been obtained from the treating physician at the hospital where the patient was identified, or from the physician who is listed as the treating physician

CONTROLS

- 1. Stratified to match cases by age (5-year intervals), gender and race
- 2. Must reside in Baltimore City or contiguous metropolitan counties, Anne Arundel and Prince George's counties, Eastern Shore, western and northern Maryland, or adjacent counties in Pennsylvania, Delaware, Virginia, or Washington DC area
- 3. Has a residential working phone within his house
- 4. Was born in the United States
- 5. Speaks English well enough to be interviewed
- 6. Is physically and mentally capable of performing the interview
- 7. Never has been interviewed as a control for the study (with our tracking database)

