3 STUDY IMPLEMENTATION

The study will be implemented in two phases. The first phase is conducted as a pilot study to evaluate recruitment procedures. The second phase is the main study that will be closed when the projected 1000 cases and 1000 controls have been enrolled. Participants in the pilot study will count toward the total accrual.

TIME SCHEDULE OF THE STUDY

Month 1	Begin pilot study
Month 13	Review and revise protocol if needed Resubmit to IRB if needed
Month 14	Begin accrual for the study at the projected rate of 80 cases* and 80 population-based controls* per year. Cases with prostatectomy and/or therapy will be eligible
Month 62*	Close enrollment if target accruals are met

* have been increased to 120 cases and 120 controls per year; now projected for 2014/15

NCI IRB Approval:	October 28, 2004
Protocol Number:	05-C-N021

PILOT STUDY (was completed in 2006)

During the 12-month pilot phase, we will recruit about 80 patients who are either African-Americans or Caucasians, and have had a radical prostatectomy and/or therapy. We will also start recruiting controls that match the cases on age (5-year intervals) and race. We will recruit the cases at the 2 participating hospitals.

We will assess the availability of PCa patients, who 1) are willing to participate in the study, 2) are of African-American descent or 3) provide tumor specimens. In this period, we expect to recruit 25 patients who will have a radical prostatectomy as the initial treatment. Approximately half of the patients should be of African-American descent. We will also assess the availability of controls that are eligible for both the lung cancer and the PCa case-control study and frequency-match the PCa cases by age and race.

The criteria that are used to determine if the pilot is successful are 1) the accrual of 80 cases and 80 matched controls, 2) the accrual of about 40 cases who are of African-American descent, and 3) the collection of 25 fresh-frozen tumor specimens. If major modifications are required to improve accrual rates or other aspects of the study, then the pilot study will be extended to address these issues. Otherwise, we will start recruiting for the main study at the projected rate of 80 cases and 80 controls per year.

PERSONNEL

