3.1.2 COLLECTION AND PROCESSING OF BIOLOGICAL SAMPLES

We will collect blood, urine, and tumor specimens. The collected blood will be used for the analysis of genotypes and the measurement of hormone, cytokine, and eicosanoid concentrations in serum and plasma. Urine samples are collected to study the association between inflammation of the prostate and the progression of the disease. The collected urine will be analyzed for markers of inflammation and oxidative stress such 8hydroxydeoxyguanosine, malondialdehyde, nitrate/nitrite, and metabolites of the eicosanoid pathway. We are also planning to measure nicotine metabolites in urinary samples to study the association between nicotine metabolism, genetic polymorphisms, and the risk of advanced prostate cancer. The tissue specimens are collected for wholegenome gene expression analysis and the preparation of tissue arrays for immunohistochemical analysis of protein expression.

The collection of blood, urine, and tissue specimens, will follow procedures that have been established for our protocol titled "Resource for the collection and evaluation of human tissues and cells from donors with an epidemiology profile", University of Maryland at Baltimore IRB #0298229. The same procedures are used in the lung cancer case-control study. For surgical specimens, each late afternoon one of the lab personnel checks the schedule for possible tissues. A note that reminds the operating room (OR) personnel to send the resected specimen to the pathology fresh, not fixed, is given to the OR. When the resection of a tumor is done, the OR will call the University of Maryland Department of Pathology. A designated person will transport the tissue to the pathology, where the tissue is procured as soon as possible. All biological samples will be stored at the pathology until further notice. The procedures are as follows.

PROCEDURES FOR COLLECTION OF BLOOD AND URINE

- 1. Observe universal precautions for prevention of transmission of blood-borne pathogens
- 2. Clean skin with alcohol wipe and wait to dry
- 3. Obtain blood: one 15 cc red top tube, two or three 10 cc green top tubes and one 10 cc red-green top tube. Apply pressure and band-aid
- 4. Place blood samples on ice
- 5. Request urine sample in plain sterile container (50 ml)

PROCEDURES FOR PROCESSING OF BLOOD AND URINE AT THE UNIVERSITY OF MARYLAND DEPARTMENT OF PATHOLOGY

- 1. Storage of urine at -70° C in 10 ml aliquots

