Another limitation relates to problems associated with rapid subject accrual. We expect to identify all cases through hospital pathology and oncology departments. This will be verified through tumor registry records at 6-months intervals. Based on our experience in the ongoing lung cancer case-control study, we expect to contact most of the subjects prior to treatment or surgery, but will confirm this during our pilot study. We will allow for accrual of subjects before and after surgery, which will give us more flexibility for the accrual process.

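### Case blood and urine may be collected after treatment, and no rule limits or adjusts the secondary IGF-1, hormone, cytokine, eicosanoid and urine marker analyses for this

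*Protocol*

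**What the plan says.** **Timing of case samples.** Section 2 (Enrollment of cases) aims to consent and interview patients well before surgery or other treatment, with blood drawn after the interview. Where that fails, the patient may be approached up to one day before surgery, and then: "We will offer to administer the questionnaire and obtain blood after the surgery". A draw on the day of consent remains possible if the patient wishes. In the case procedures, urine collection is the step after blood. Section 3.1.5 confirms: "We will allow for accrual of subjects before and after surgery, which will give us more flexibility for the accrual process".

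**Who qualifies.** The first case criterion in section 2.1.1 is "Has been diagnosed with PCa within the last two years". The time schedule in section 3 says "Cases with prostatectomy and/or therapy will be eligible". Section 1.2.1 expects up to 25 prostatectomy patients a year, operated on before any other therapy, and adds: "The remaining patients will have chemotherapy, radiation, or hormone therapy, where only blood samples but no tumor specimens will be collected". No time point is set for those blood samples.

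**What is measured.** Section 3.1.2 lists "the measurement of hormone, cytokine, and eicosanoid concentrations in serum and plasma", together with urinary inflammation, oxidative-stress and nicotine markers. A secondary objective in section 1.1 reads: "We will determine IGF-1 serum concentrations in our study population and compare gene expression profiles of about 10-15 low-stage tumors". The tumors come from patients in the extreme IGF-1 quartiles. Section 1.2.5 correlates IGF-1 bioavailability with tissue markers of Akt activation. Section 3.1.2 links urine markers of prostate inflammation to progression. Section 5.4.3 places blood hormone concentrations in case-case analyses.

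**What is recorded.** Section 5.1.3 stores a procurement date for tissue and blood; urine is not named. Section 3.1 provides for abstraction of medical and pathology records without naming treatment dates.

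**The concern.** Germline genotype is the same before and after treatment, so the primary objective does not depend on when blood is drawn. Serum, plasma and urine concentrations can depend on it. The IGF-1 hypotheses concern the level present while the tumor was in place. A level measured after the tumor has been removed is a different quantity, yet the protocol would use it to sort that tumor into a quartile group or to correlate with its tissue markers.

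The surgical exception also falls on the men who matter most here. Section 2 justifies late approach by the need for fresh-frozen tumors, so a man sampled after surgery is likely to be a tumor donor.

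For urine and hormones the risk is confounding. If treatment changes the marker and treatment differs by stage or course of disease, an association with stage or progression may reflect treatment. A urine sample taken after prostatectomy also cannot show inflammation in a gland that is no longer there.

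**Working it through.** **Is there any rule on timing?** The protocol states no figure on this point, so there is nothing to reproduce. The relevant places compare as follows:

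- Sections 2, 2.1.1, 3 and 3.1.5 permit post-surgical draws, treated cases and a two-year window.
- Sections 1.1, 1.2.5, 3.1.2 and 5.4.3 use the resulting marker values. None requires a pre-treatment sample. Section 5.4.3 speaks only generally of adjusting for possible confounders.
- Section 3.1.5 expects to reach most subjects before treatment and says the pilot will confirm it. The pilot success criteria in section 3 omit this, and no result is given although the pilot is marked complete. Draw timing is not among the items singled out for monitoring in section 5.6.
- Section 2 allows a redraw, for example after a highly unusual laboratory result. Section 3.1 starts laboratory work at the end of recruitment, so such a redraw may fall long after treatment.

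**How many cases come through the non-surgical route?** With 25 prostatectomy cases a year and 80 to 120 cases accrued, (80 − 25)/80 = 69% to (120 − 25)/120 = 79%, if the 25 stays fixed. This is the share with no stated draw time. It is not an estimate of the share sampled after treatment.

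**Effect on IGF-1 quartiles within cases.** Assumptions, none from the protocol: a normal marker with SD 1; a random share f of case samples is post-treatment; treatment lowers the value by d SD; quartiles are cut among cases. Observed value = pre-treatment value − d × (1 if post-treatment, otherwise 0). Results are from 1,000,000 simulated cases per setting. The last column multiplies the misplaced share by groups of 10 and 15 tumors. An upward shift gives the mirror image.

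| f | d (SD) | Post-treatment share, lowest / highest quartile | Lowest quartile correctly placed | Misplaced tumors of 10–15 |
|---|---|---|---|---|
| 10% | 0.2 | 12.5% / 7.8% | 97.6% | 0.2–0.4 |
| 10% | 0.5 | 16.4% / 5.1% | 93.7% | 0.6–0.9 |
| 10% | 1.0 | 23.2% / 2.2% | 86.8% | 1.3–2.0 |
| 25% | 0.2 | 29.8% / 20.3% | 95.1% | 0.5–0.7 |
| 25% | 0.5 | 37.7% / 14.3% | 87.4% | 1.3–1.9 |
| 25% | 1.0 | 50.9% / 6.7% | 74.1% | 2.6–3.9 |
| 50% | 0.2 | 56.5% / 43.8% | 93.7% | 0.6–0.9 |
| 50% | 0.5 | 65.7% / 34.6% | 84.5% | 1.6–2.3 |
| 50% | 1.0 | 79.2% / 20.6% | 70.6% | 2.9–4.4 |

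Two things happen together: some tumors are misplaced, and the low and high groups come to differ in treatment timing.

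**Effect on stage or progression comparisons.** If the post-treatment share is f₁ in one stage group and f₂ in the other, the spurious mean difference is (f₁ − f₂) × d. With assumed shares of 50% and 25% and d = 0.5, this is 0.25 × 0.5 = 0.125 SD.

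**If a case-control marker test were added.** Controls with prior radiation or chemotherapy are excluded (section 2.1.2), so those effects could occur only in cases. At 1000 per group with no true difference, bias = f × d, z = f·d / (s·√(2/1000)) with s² = 1 + 0.5·f(1 − f)·d², and the chance of a false significant result at two-sided 0.05 is Φ(z − 1.96) + Φ(−z − 1.96).

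- f = 10%, d = 0.2: z = 0.45, 7%.
- f = 25%, d = 0.5: z = 2.76, 79%.
- f = 50%, d = 0.5: about 100%.
- f = 0: 5%.

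The protocol does not write this test out, so these figures apply only if someone runs it.

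**The case against.** A reader might infer that these markers are compared with controls and that treatment effects will be reported as disease biology. The documents do not support that.

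- **Control comparison.** Every marker analysis the protocol names is within cases. IGF-1 is to be measured in the study population, and section 5.4.3 describes odds ratios for risk factors, so a control comparison is possible. None is specified for IGF-1, hormones, cytokines or urine markers.
- **Frequency.** The post-surgical draw is an exception. Pathology departments are checked daily, cases are incident, and sections 2 and 3.1.5 expect most patients to be reached before treatment. Sampling during therapy is allowed by the eligibility rules but never stated as a plan.
- **Tumor tissue.** Donors have surgery before other therapy (section 1.2.1), so later treatment cannot alter the expression profile. Only the paired blood or urine value is exposed.
- **Analysis detail.** Which samples enter a secondary marker analysis is often left to an SAP, and the stored blood date may allow timing to be reconstructed if treatment dates are abstracted.

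The first three points stand and limit the claim. The last stands in part. An SAP could add an adjustment, but this protocol itself sets the open sampling window, and no analysis can recover a pre-treatment sample that was never drawn. The expectation in section 3.1.5 carries no number or threshold, and no reported result supports it.

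**Conclusion.** The point holds for the secondary marker analyses. As written, the plan lets post-treatment blood and urine enter them without restriction, stratification or named adjustment. Treatment effects may then be mistaken for disease biology: IGF-1 quartile groups may be misassigned, IGF-1/Akt correlations blurred, and urine or hormone associations with progression or stage confounded. Any case-control marker comparison would carry the same bias. The germline genotype analyses are untouched.

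The size cannot be fixed from the documents. Over the assumed range (10% to 50% of samples post-treatment, shift 0.2 to 1.0 SD), between 2% and 29% of the lowest IGF-1 quartile is misplaced. That is negligible at one end and 3 to 4 tumors of 10 to 15 at the other. Nothing in the protocol shows where in that range the study lies.

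**What to change.** 1. Record the draw date and treatment status (surgery, radiation, chemotherapy, hormone therapy) for every case blood and urine sample, including redraws. Extend the stored procurement date to urine, and abstract treatment dates from the records.
2. Base the main serum, plasma and urine marker analyses on samples taken before any treatment. This includes the IGF-1 quartile grouping and the tissue correlations.
3. Report all samples as a sensitivity analysis, with treatment status as an adjustment or stratification factor. Genotype analyses keep every case.

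**Cost.** Recording is cheap, since blood dates are stored and records are already abstracted. The real cost is numbers. Table 6 plans 40 to 60 low-stage tumors, so an extreme quartile holds 10 to 15. Losing an assumed 10% of donors leaves 9 to 13.5 per quartile, and losing 25% leaves 7.5 to 11.25, against the protocol's own best estimate of 13 per group in section 5.4.1. This is why the treated samples should stay in a sensitivity analysis and not be discarded. If most subjects are reached before treatment, as section 3.1.5 expects, the loss is small.
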